6.7 Missing Data for Efficacy and Safety Endpoints

Missing data for each efficacy endpoint will be handled as described in Sections 9.1 and 9.3.4.

For continuous endpoints, change from baseline will be set to missing at visits with missing postbaseline values or where data were imputed to missing. Continuous efficacy endpoints will be set to missing for subjects who received any of the following not allowed medication post-baseline procedure:

- Corticosteroids (e.g., oral, parenteral or injection, budesonide or other sinus steroid irrigations/rinses or drops, breath powered Xhance, nebulized steroids administered nasally or other drug eluting stents) through Day 45; or
- Biologics for CRS treatment (e.g., Dupixent).

For binary endpoints, subjects with missing efficacy data, early withdrawals, and/or subjects who received not allowed corticosteroids or biologics for chronic sinusitis condition attributable to the FSO/frontal recess will be imputed as a treatment failure. If a subject initiates high-dose steroid for other reasons not involving FSO/frontal recess, this does not represent treatment failure.

Additional rules for handling of missing data and rescue treatments are detailed below:

- *Missing efficacy data.* Visits with missing data (due to a missed visit or missing component of a composite endpoint) will be set to treatment failure.
- *Early withdrawals.* Only visits following the early withdrawal visit will be set to treatment failure.
- *Rescue treatments.* Subjects who rescue with corticosteroids (before Day 45) or biologics will be set to treatment failure at all subsequent visits and continuous endpoints set to missing.
- *Missing baseline value.* For efficacy endpoints, a missing value at baseline will not be imputed, and the endpoint will be set to missing for all visits.

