9 EFFICACY ANALYSES

9.1 General Considerations

Missing data imputation analyses:

- *Observed case (OC)*. Missing values remain missing. For the categorical composite endpoints, in the case that some components are missing, the composite endpoint assessment will be derived based on the non-missing components. If non-missing components are not sufficient to determine final composite endpoint, then the composite endpoint will be set as missing. For continuous composite endpoints, if any components are missing, the composite endpoints will be set as missing.
- *Last observation carried forward (LOCF)*. Baseline measurements will not be carried forward to post-baseline. Only post-baseline measurements will be LOCF. For the composite

endpoints, the last non-missing post-baseline observation will be carried forward to subsequent visits for each individual component first, and then the composite endpoints using individual components imputed by LOCF will be calculated as described above. If a subject does not have a non-missing observed record for a post-baseline visit, the last post-baseline record prior to the missed visit will be used for this post-baseline visit. If the last non-missing observation prior to the missing visits cannot be determined due to multiple measurements occurring at the same time or the time not available within the same day, the worst outcome will be used for LOCF. If missing components still exist after LOCF, the composite endpoints will be calculated using the same rules as described in OC.

- *Non-responder imputation (NRI)*. For all binary response measurements, starting from OC, all missing values will be set as non-responders. If subject only had baseline measurements, LOCF and OC analyses will not include this subject. But this subject will be treated as non-responder in NRI analyses.

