9.2.3 Need for Post-operative Intervention

Need for post-operative intervention is determined by clinical investigators at Day 21, 45, 90, and 180 as follows:

- Repeat frontal BSD warranted or performed for restenosis/occlusion in the frontal recess/FSO; or
- Surgical intervention warranted or performed to debride obstructive adhesions/scarring or for restenosis/occlusion in the frontal recess/FSO; or
- Oral steroids warranted or prescribed to resolve recurrent edema in the frontal recess/FSO.

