9.4.1 Multiplicity Adjustment for Key Secondary Endpoints

Intersect ENT intends to present inferential statistical results to support product labeling claims for 5 key secondary endpoints. This section describes the methods that will be used to control the familywise type 1 error rate (FWER) among the tests of these 5 secondary endpoints. All other secondary endpoints will be viewed as exploratory or explanatory in nature.

1. Cross-sectional area of the FSO change from baseline to Day 45 on CT by an independent, blinded reviewer
Test: $H_0: \mu = 0$ vs $\mu \neq 0$ by t-test
2. FSOT at Day 45 on CT by an independent, blinded reviewer
Test: $H_0: \mu = 0$ vs $\mu \neq 0$ by t-test
3. FSO minimum diameter at Day 45 on CT by an independent, blinded reviewer
Test: $H_0: \mu = 0$ vs $\mu \neq 0$ by t-test
4. Zinreich's modified Lund-Mackay score for frontal sinus at Day 45 on CT by an independent, blinded reviewer
Test: $H_0: \mu = 0$ vs $\mu \neq 0$ by t-test
5. Need for post-operative intervention by clinical investigators at Day 45

Test: $H_0: p_T = p_C$, where p_T and p_C are the probability of needing post-operative intervention on the treatment and control sides, respectively. Tested by McNemar's test (exact version).

Let $p_{(1)} \leq p_{(2)} \leq \dots \leq p_{(m)}$ be the $m=5$ p-values resulting from the above 5 tests, after being placed in ascending order. Adjusted p-values $\tilde{p}_{(1)}, \dots, \tilde{p}_{(m)}$ from Holm's step-down procedure will be calculated as follows:

$$\tilde{p}_{(i)} = \begin{cases} mp_{(1)} & \text{for } i = 1 \\ \max\left(\tilde{p}_{(i-1)}, (m-i+1)p_{(i)}\right) & \text{for } i = 2, \dots, m \end{cases}$$

Source: SAS Institute Inc. 2008. *SAS/STAT® 9.22 User's Guide*. Cary, NC: SAS Institute Inc., p 4839.

If any adjusted p-value exceeds 1, it is set to 1. Using this procedure, any adjusted p-value that is < 0.05 is statistically significant and supports a claim for the corresponding endpoint, while any

CONFIDENTIAL

25 of 33

May not be reproduced outside of Intersect ENT without written permission from Document Control

adjusted p-value ≥ 0.05 is not statistically significant. Both adjusted and unadjusted p-values will be reported.

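### SAP 6.7 assigns treatment failure to the subject without naming a side, so a one-sided need treated with steroids before Day 45 drops out of the between-side test of key secondary 5

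*SAP*

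**What the plan says.** **Failure rules (SAP 6.7).** For binary endpoints, "subjects who received not allowed corticosteroids or biologics for chronic sinusitis condition attributable to the FSO/frontal recess will be imputed as a treatment failure". The bullets beneath add that those who "rescue with corticosteroids (before Day 45) or biologics will be set to treatment failure at all subsequent visits and continuous endpoints set to missing". For missing data, "Visits with missing data (due to a missed visit or missing component of a composite endpoint) will be set to treatment failure". Visits after an early withdrawal are also set to failure. None of these rules mentions a side.

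**Endpoint (SAP 9.2.3 and 9.4.1).** Need for post-operative intervention is met by any one of three components: repeat balloon dilation, surgical intervention, or "Oral steroids warranted or prescribed to resolve recurrent edema in the frontal recess/FSO". Key secondary 5 tests whether two probabilities are equal; these "are the probability of needing post-operative intervention on the treatment and control sides, respectively". The test is exact McNemar. Its p-value enters a Holm procedure with four others, and an adjusted p below 0.05 supports a labelling claim.

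**Missing components (SAP 9.1).** Section 6.7 opens with "Missing data for each efficacy endpoint will be handled as described in Sections 9.1 and 9.3.4". In 9.1, under the observed-case method, "the composite endpoint assessment will be derived based on the non-missing components". Section 9.1 describes observed case, LOCF and non-responder imputation, and does not say which is the main method for key secondary 5.

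**Missing baseline (SAP 6.7).** "For efficacy endpoints, a missing value at baseline will not be imputed, and the endpoint will be set to missing for all visits".

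**Primary endpoint.** Section 6.7 sets continuous endpoints to missing after a disallowed steroid or biologic. Section 9.3.4, headed as sensitivity analyses, imputes the area by side after oral steroids or revision surgery, and says that no other imputation rules apply in the planned analyses.

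**The concern.** Each subject supplies both arms of this trial, so a rule that fails the subject does not define the outcome of a comparison between sides. The literal reading is that both sides fail.

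That reading discards information the endpoint is meant to capture. If frontal edema recurs on one side only and is treated with oral steroids before Day 45, the steroid need is itself a component of the endpoint on that side. Section 6.7 then fails the other side too. The discordant pair becomes concordant, and McNemar's test ignores concordant pairs. The realistic choice is between failing both sides and failing the recorded side, and the SAP does not make it for this endpoint. Section 9.3.4 does separate sides after an intervention, but only for cross-sectional area.

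A claim intended for labelling could therefore rest on a coding choice made after the data are seen.

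**Working it through.** **1. The plan's own figures.** The SAP gives no expected rates, rescue frequency or power for key secondary 5, so there is nothing to reproduce for it. The primary sample size reproduces: with a difference of 9 mm² and SD 18 mm², a paired t-test at two-sided 0.05 needs 54 subjects for 95% power, and the stated 56 give 95.7%. That figure is not in dispute.

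**2. What the literal coding does, event by event.**
- Missed visit or withdrawal, both sides failed: the pair is concordant, so the McNemar p-value is unchanged.
- Steroid rescue before Day 45 for a one-sided need: discordant if coded by recorded side, concordant under 6.7 read literally. The test changes.
- Need first recorded at Day 45, or met by repeat dilation or surgery without steroids or biologics: not covered by the rescue bullet. No change.

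**3. Size, with assumed counts.** Let b be the smaller and c the larger discordant count, and n = b + c. The exact two-sided p is 2 × Σ(i = 0 to b) C(n, i) / 2ⁿ. The Holm multiplier is 5 if this is the smallest of the five p-values and 1 if it is the largest.

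| Coding | Treatment-only v control-only | Arithmetic | p | × 5 |
|---|---|---|---|---|
| Recorded side | 2 v 14 | 2(1+16+120)/65,536 | 0.0042 | 0.021 |
| One control-only pair to both sides | 2 v 13 | 2(1+15+105)/32,768 | 0.0074 | 0.037 |
| Two control-only pairs to both sides | 2 v 12 | 2(1+14+91)/16,384 | 0.0129 | 0.065 |
| Two control-only and one treatment-only pair to both sides | 1 v 12 | 2(1+13)/8,192 | 0.0034 | 0.017 |

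The third row crosses 0.05 at multiplier 5 and the fourth crosses back. At multiplier 1 all four rows stay below 0.05.

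**4. Missing component.** The endpoint is met if any component is met, so 6.7 and 9.1 agree whenever a recorded component is positive. They differ when the recorded components are negative and one is missing. Take a recorded need on the control side and one component missing on the treatment side. Under 6.7 the visit fails and the pair is concordant. Under observed case the treatment side is derived from what was recorded, giving a discordant pair, or it is missing if the rest is judged insufficient.

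**5. Missing baseline.** The primary endpoint, FSOT volume, minimum diameter and Zinreich score are all compared between sides at Day 45 (9.3.1, 9.4). None uses a baseline value, yet the 6.7 rule as worded would delete them. Only the change-from-baseline endpoints need it.

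**6. Primary endpoint.** Assume 64 measured pairs (80 × 0.80), mean 9, SD 18, and 8 subjects rescued.
- Areas kept: t = 9/(18/√64) = 4.00, p = 0.0002.
- Eight set to missing, same mean: t = 9/(18/√56) = 3.74, p = 0.0004.
- Eight differences set to zero: mean 9 × 56/64 = 7.9, SD 17.1, p = 0.0005.

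If the eight removed average 0, the remaining mean is 576/56 = 10.3. If they average 18, it is (576 − 144)/56 = 7.7. The estimate moves, but at the design effect the conclusion does not.

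**The case against.** **The affected group is narrow.** The rescue rule bites only on steroid or biologic use before Day 45. It applies equally to treatment-only and control-only needs, so it does not work in one direction. This stands. It is why the table includes a row with recoding on both sides, and why no count of recodings can be given at which the claim is lost.

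**Stronger readings that a reader might infer, which the documents do not support:**
- *A control-only need could be coded to the treated side, or two analysts could code one rescue to opposite sides.* No passage moves a control-side event to the treated side. Section 6.7 read literally means both sides. The one side-specific rule, in 9.3.4, sets the control area to zero after a control-only intervention.
- *Failing missed visits on both sides would dilute the reported benefit.* SAP 6.1 summarizes this endpoint by subjects providing data, and 6.8 limits summary tables to completed scheduled visits. Imputed failures may therefore never enter the tabulated rates.
- *Side may not be recorded for steroid need.* SAP 9.8 mentions side only for surgical intervention. However, Protocol 16.1 says that medical or surgical need is captured on the endoscopic CRF, and 9.3.4 presumes that the side of an oral-steroid intervention is known. Confirmation is enough.

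**Primary endpoint.** The heading of 9.3.4 and the separate Sensitivity column in Table 1 suggest that 6.7 governs the main analysis and 9.3.4 is sensitivity. That is the likely reading, but the opening sentence of 6.7 and the closing rule of 9.3.4 leave it unstated.

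**Missing baseline.** A screening CT is required for eligibility (Protocol 11.1), so few subjects should be affected. This also stands.

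**Conclusion.** The concern holds for key secondary 5. The SAP's failure rule is written for subjects and visits, while the endpoint is defined by side. Applied literally, the rule removes one-sided needs treated with steroids before Day 45 from the test. Confidence is high on the text and low on the size. The counts are assumptions, and the result depends on how many treatment-only and control-only needs are recoded. In the illustration the p-value at multiplier 5 runs from 0.017 to 0.065, so the labelling claim can turn on the coding in either direction; it does not follow that the claim would be lost.

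The conflict between 6.7 and 9.1 on missing components and the over-wide missing-baseline rule are real but smaller. The precedence of 6.7 and 9.3.4 for the primary t-test needs one clarifying line and changes no conclusion at the design effect. This should be fixed, ideally before the Day 45 data are unblinded.

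**What to change.** 1. For key secondary 5, assign failure only to the side or sides recorded as needing intervention and keep the other side's recorded value. Treat both sides as failed only when no side is recorded.
2. Name one main missing-data rule for this endpoint. It should settle 6.7 against 9.1 for missing components and missed visits, with the alternative as a sensitivity analysis.
3. Limit the missing-baseline rule to change-from-baseline endpoints.
4. Add one line stating that 6.7 governs the primary t-test and 9.3.4 is sensitivity, or the reverse.
5. Confirm that the endoscopic CRF records side for oral-steroid need.

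The cost is SAP wording and one additional run of a simple test. A query to sites or a CRF change would arise only if item 5 shows that side is not captured.

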4.2 Study Design

This is a post-market, randomized, intra-patient controlled, blinded, multicenter trial enrolling up to 80 randomized subjects from up to 20 US sites. Study subjects will be randomized following a successful in-office bilateral frontal BSD to receive 1 PROPEL Contour on 1 FSO side (treatment), and nothing on the contralateral side (the control treatment).

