6 STATISTICAL METHODS

6.1 General Considerations for Data Analysis

All analyses described in this plan are considered a priori analyses in that they have been defined prior to locking the database and reviewing unblinded results. All other analyses, if any, designed subsequent to locking the database will be considered post-hoc analyses and will be considered exploratory. Any post hoc analyses will be clearly identified in the clinical study report.

Continuous data such as cross-sectional area of FSO, FSO minimum diameter, FSOT volume, inflammation score, CRS side-specific symptom score, SNOT-22 score, and RSI score will be summarized in terms of the mean, standard deviation (SD), median, minimum, maximum, and number of observations, unless otherwise stated.

Categorical data such as Lund-Mackay score, Zinreich's modified Lund-Mackay score, adhesion/scarring grade, polypoid edema grade, and polyp grade will be analyzed quantitatively and summarized in terms of the mean, standard deviation (SD), median, minimum, maximum, and number of observations, unless otherwise stated.

Categorical data such as need for post-operative intervention in the frontal recess/FSO, patient satisfaction, implant delivery success rate, and economic measures will be summarized in terms of the number of subjects providing data at the relevant time point, frequency counts and percentages. If not stated otherwise, percentages will be presented with one decimal place. Percentages will not be presented for zero counts. Percentages will be calculated using n as the denominator. 100% will be presented without decimal places. Frequency distributions showing

findings by treatment side will be presented with counts, percentages and, where appropriate, exact 95% CI using the Clopper and Pearson method.

P-values greater than or equal to 0.001, in general, will be presented to 3 decimal places. P-values less than 0.001 will be presented as “< 0.001”.

95% Confidence intervals (CI) will be presented to 1 more decimal place than the raw data. Unless stated otherwise, a two-sided 95% confidence level will be calculated when confidence interval is presented.

Data from the protocol-specified visits (i.e., as reported in the case report form, CRF) will be used in the summary tables and data listings.

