9.2.4 Patient-Reported Outcomes

9.2.4.1 SNOT-22 Questionnaire

The Sino-Nasal Outcome Test (SNOT-22) questionnaire is a validated, disease-specific, symptom-scoring instrument consisting of 22 questions, each scored by patient on a 6-point scale as follows:

- 0: No problem
- 1: Very mild problem
- 2: Mild or slight problem
- 3: Moderate problem
- 4: Severe problem
- 5: Problem as bad as it can be

The maximum total score for all symptoms is equal to 110. The total SNOT-22 scores and individual domain scores will be computed. The total score is calculated as the sum of all 22 items, and ranges from 0 to 110, with the higher scores being worse outcome. The following **Table 3** lists items and ranges for each symptom domain score.

Table 3: SNOT-22 Domain Scoring

SNOT-22 Domain	Survey Item	Score Range
Rhinologic Symptoms	1, 2, 3, 6, 21, 22	0–30
Extra-Nasal Rhinologic Symptoms	4, 5, 6	0–15
Ear/Facial Symptoms	2, 7, 8, 9, 10	0–25
Psychological Dysfunction	14, 15, 16, 17, 18, 19, 20	0–35
Sleep Dysfunction	11, 12, 13, 14, 15	0–25

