9.2.4.2 RSI Questionnaire

The Rhinosinusitis Symptom Inventory (RSI) is administered using a paper (reflective) questionnaire to assess the CRS symptoms: 5 key symptoms (facial pain/pressure, facial congestion/ fullness, nasal obstruction/blockage, nasal discharge or post-nasal drip, decreased sense of smell), 7 other symptoms (headache, halitosis, dental pain, cough, ear symptoms, fevers, and fatigue) on a 6-point scale of 0 to 5, as follows:

- 0: Absent
- 1: Very mild
- 2: Mild
- 3: Moderate
- 4: Severe
- 5: Very severe

The total symptom scores and individual domain scores will be computed. The total score is calculated as the sum of all 12 symptom scores. The individual symptom scores are used to calculate 4 domain scores (**Table 4**).

Table 4: RSI Domain Scoring

RSI Domain	Symptom	Score Range
Nasal symptoms	Nasal obstruction Rhinorrea Sense of smell	0–15
Facial symptoms	Facial pain/pressure Facial congestion/fullness Headache	0–15
Otolaryngologeal symptoms	Halitosis Dental pain Cough Ear symptoms	0–20
Systemic	Fevers Fatigue	0–10

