9.2.4.3 CRS Side-Specific Questionnaire

The CRS side-specific Questionnaire allows patients to evaluate each of the following 5 cardinal symptoms of CRS on the left and right side:

- Facial pain/pressure

- Facial congestion/fullness
- Nasal obstruction/blockage
- Discolored or pus nasal discharge or post-nasal drip
- Decreased sense of smell

Each side is scored individually on a 6-point scale as follows:

- 0: Absent
- 1: Very mild
- 2: Mild
- 3: Moderate
- 4: Severe
- 5: Very severe

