9.5 Secondary Endpoint Analysis

Secondary endpoints to be collected and analyzed are listed below alongside references to the sections in which they are defined:

CT grading by an independent, blinded reviewer (see Section 9.2.1):

- Cross-sectional area of FSO (Day 180) and change from baseline
- FSOT volume (Day 180) and change from baseline
- FSO minimum diameter (Day 180) and change from baseline
- Zinreich's modified Lund-Mackay score for the frontal sinus (change from baseline to Day 45)
- Zinreich's modified Lund-Mackay score for the frontal sinus (Day 180) and change from baseline
- Lund-Mackay score for the frontal sinus (Day 45, 180) and change from baseline

CT grading by clinical investigators (see Section 9.2.1):

- Lund-Mackay score for the frontal sinus (Day 45, 180) and change from baseline

Endoscopic grading by clinical investigators (see Section 9.2.2):

- Need for post-operative intervention in the frontal recess/FSO as determined by clinical investigators (Day 21, 90, 180)
- Adhesion/scarring grade in the frontal recess/FSO (Day 21, 45, 90, 180):
- Adhesion/scarring grade in the ethmoid sinus (Day 21, 45, 90, 180):
- Inflammation score in the frontal recess/FSO (Day 21, 45, 90, 180):
- Polypoid edema in the frontal recess/FSO (Day 21, 45, 90, 180):

Patient-reported outcomes (see Section 9.2.4):

- CRS side-specific questionnaire (Day 21, 45, 90, 180)
- SNOT-22 score (Day 180)
- RSI score (Day 180)

Implant delivery success rate (see Section 9.2.5)

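### SAP 6.7 removes observed Day 180 SNOT-22 and RSI scores after early corticosteroids or any biologic, so two whole-patient summaries with no control side are selected on a symptom-related post-baseline event

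*SAP*

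**What the plan says.** **The scores.** For SNOT-22, SAP 9.2.4.1 states: "The total score is calculated as the sum of all 22 items, and ranges from 0 to 110". For RSI, SAP 9.2.4.2 states: "The total score is calculated as the sum of all 12 symptom scores". Neither is split by side. Only the CRS side-specific questionnaire is; of it SAP 9.2.4.3 says "Each side is scored individually on a 6-point scale as follows".

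**The design.** SAP 4.2 randomizes each subject "to receive 1 PROPEL Contour on 1 FSO side (treatment), and nothing on the contralateral side". SAP Table 2 reports SNOT-22 and RSI on the PTE population only, and PTE requires that the implant was received.

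**Timing.** Both schedules of assessments (Protocol Section 7, SAP Appendix A) place the two questionnaires at baseline and Day 180 only. SAP 9.5 lists Day 180 for each.

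**Classification.** Under continuous data, SAP 6.1 says "CRS side-specific symptom score, SNOT-22 score, and RSI score will be summarized in terms of the mean" and other descriptive statistics. Both scores are defined and analysed within SAP Section 9, Efficacy Analyses.

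**The deletion rule.** SAP 6.7 sets continuous efficacy endpoints to missing for subjects who received listed corticosteroids through Day 45, or biologics for CRS. It names no visit to which this is limited. Its rescue bullet repeats the rule: such subjects "rescue with corticosteroids (before Day 45) or biologics will be set to treatment failure at all subsequent visits and continuous endpoints set to missing".

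**The steroid restriction.** Protocol Section 14 bars these corticosteroids through Day 45 unless clinically necessary, and gives unbiased assessment of the primary endpoint as the reason. Protocol 15.1 states the exception more narrowly: increased or persistent frontal inflammation together with symptoms that lead the patient to ask for treatment.

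**The concern.** When a patient drops out of a side-to-side comparison, both sides leave together. A whole-patient score with no control has no such balance, so whoever is removed changes the reported mean directly.

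The removal is triggered by an event after baseline, and Protocol 15.1 makes symptoms part of the condition for that event. The endpoint being filtered is itself a symptom score. If patients treated early with steroids tend to do worse, the Day 180 summary will look better than the outcome of all patients who returned the questionnaire.

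The rule also fits the endpoint poorly. The Day 45 limit protects a CT measurement taken at Day 45. Applied to a Day 180 questionnaire, it deletes a score for a short steroid course given months before, yet does nothing about a corticosteroid first used after Day 45, even one in use at the Day 180 visit.

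At stake is the credibility of two descriptive patient-reported summaries. The trial's main inference is not at stake.

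**Working it through.** The plan gives no figure for SNOT-22 or RSI (no mean, SD or expected rescue rate), so there is nothing of its own to reproduce here. The check has three parts.

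**1. Does the rule reach these scores, and does anything restore them?**

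- They are continuous (SAP 6.1) and lie within the efficacy section (SAP Section 9), so 6.7 applies as written. The only scheduled post-baseline value is Day 180, so that is the value lost.
- Observed case (SAP 9.1) leaves missing values missing.
- LOCF (SAP 9.1) does not carry baseline forward, and there is no earlier scheduled post-baseline score.
- Non-responder imputation (SAP 9.1) is for binary measures.
- Protocol 12.5 permits questionnaires at unscheduled visits, but SAP 6.8 keeps those visits out of summary tables.
- The sensitivity analyses in SAP 9.3.4 concern the primary endpoint only.

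Nothing restores the score. The rule also sits awkwardly with SAP 6.1, which says that all available data at each time point will be presented.

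**2. Who is removed and who is kept?**

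| Exposure after the procedure | Day 180 score under 6.7 |
|---|---|
| Listed corticosteroid through Day 45, any indication | Removed |
| Same, continued to Day 180 | Removed |
| Corticosteroid first used after Day 45, even if current at Day 180 | Kept |
| Biologic for CRS, at any time | Removed |

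The binary rule in 6.7 counts a steroid as failure only if it was for the FSO or frontal recess. The continuous rule has no such limit.

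Distance in time from the end of the steroid window:

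- nominal: 180 − 45 = 135 days;
- earliest allowed Day 180 visit: 180 − 14 = Day 166, and 166 − 45 = 121 days.

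**3. How far could the mean move?**

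Let f be the fraction deleted, K the mean improvement in patients kept and D the mean improvement in patients deleted. The mean over all patients is (1 − f)K + fD, while the plan reports K. The shift is therefore

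K − [(1 − f)K + fD] = f × (K − D) = f × gap.

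Both f and the gap are assumptions. Counts are shown out of 80 randomized; PTE may be smaller. Shifts are in SNOT-22 points:

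| f (patients of 80) | gap 0 | gap 5 | gap 10 | gap 20 |
|---|---|---|---|---|
| 5% (4) | 0 | 0.25 | 0.5 | 1.0 |
| 10% (8) | 0 | 0.5 | 1.0 | 2.0 |
| 20% (16) | 0 | 1.0 | 2.0 | 4.0 |

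The range is 0 to 0.20 × 20 = 4 points on a scale of 0 to 110. A negative gap, with deleted patients doing better, would reverse the sign. RSI follows the same formula with its own gap, on a scale of 0 to 12 × 5 = 60.

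**The case against.** **Low consequence.** SAP 9.4.1 places both scores outside the five Holm-adjusted endpoints and treats them as exploratory or explanatory. No test is named and no labelling claim rests on them. Steroid use through Day 180 is tabulated under SAP 9.8, and concomitant medications are listed under SAP 9.9. This stands, and it limits the weight of the point.

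**Distant exposure out, current exposure in.** A reader might infer that the rule always deletes for a remote exposure and keeps a current one. The documents do not support that. Biologics for CRS trigger deletion at any time, so a patient on one at Day 180 is removed, as is a patient whose steroids began by Day 45 and continued. The contrast holds only for corticosteroids first used after Day 45.

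**Known favourable bias.** A reader might also infer that the result is certainly flattered. Protocol 15.1 makes that direction likely, because early steroids are tied to symptoms. It is not shown: no score by rescue status is given, and patients given a listed steroid for an unrelated reason are deleted too.

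**No change from baseline.** SAP 9.5 attaches that phrase to every CT line but not to SNOT-22 or RSI, which might suggest that improvement will not be reported. The endoscopic lines and the side-specific questionnaire lack the phrase too, SAP 6.7 presupposes change scores for continuous endpoints, and both questionnaires are collected at baseline. This is missing detail, not an omitted analysis.

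**Keeping everyone is also a choice.** Including all scores credits any benefit of rescue medication to an uncontrolled mean. That is true, and is the reason to show both analyses.

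**Conclusion.** The point holds as a recommended change of modest weight. Followed as written, SAP 6.7 discards observed Day 180 SNOT-22 and RSI scores from patients defined by a post-baseline event that Protocol 15.1 links to symptoms, in summaries with no control side to absorb the loss. The Day 45 steroid window was chosen for a Day 45 CT endpoint and has no evident rationale for a questionnaire 121 to 135 days or more after it closes.

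The selection follows from the text. Its effect on the mean does not. It is 0 to 4 SNOT-22 points if 5% to 20% of patients are deleted and the gap in mean change is 0 to 20 points, all of which are assumptions. The primary and key secondary conclusions are untouched.

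**What to change.** - In SAP 6.7, exempt SNOT-22 and RSI from the set-to-missing rule.
- In SAP 9.5, summarise all reported Day 180 scores and their paired change from baseline (total and domains) with a 95% CI, regardless of rescue, and label them as uncontrolled.
- Keep the present deletion rule as a sensitivity analysis. Report how many patients it excludes, and how many used a steroid or biologic before Day 180.
- Assigning zero change to rescued patients is not needed. If wanted, make it optional, since it would flatter any patient who worsened.
- Reconcile the two steroid windows in 6.7, which are worded once as through Day 45 and once as before Day 45.

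The cost is SAP wording and one or two summary lines. No new data are needed and no clinical rule changes. The downside is that the reported mean may be less favourable and will include any benefit from rescue medication; the sensitivity analysis shows how much the choice matters.
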